8.8.7 AE Grading Scale

Severity is a measure of intensity where seriousness is defined by the criteria listed below. An AE of severe intensity may not always be considered serious. For example, nausea that persists for several hours may be considered severe nausea, but not a SAE. On the other hand, a stroke that results in only a limited degree of disability may be considered a mild stroke but would be a SAE. AEs which are not serious but which lead to permanent discontinuation of study medication will be captured in the CRF, but do not require expedited reporting. Non-serious AEs which do not lead to discontinuation of study medication will not be collected.

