8 DATA SAFETY MONITORING PLAN

8.1 Oversight

- 8.1.1 The principal investigator holds ultimate responsibility for the oversight and execution of the data and safety monitoring plan. This research site will be fully committed in the ongoing review and refinement of the trial's processes to assure subject safety, data validity and integrity, and regulatory compliance.
- 8.1.2 The principal investigator and medical monitor will monitor the safety data, assure protocol compliance, and conduct safety reviews to protect each subject's safety and welfare in this clinical investigation. The review process will be initiated after enrolling the first 10 subjects and every 10 subjects thereafter. The principal investigator will evaluate whether the study should continue unchanged, require modification, or closed to enrollment. [name] will serve as medical monitor and review all study related adverse events.
- 8.1.3 Case report forms (CRF) will be completed to capture protocol data. Two study coordinators will do separate CRF audits to assure data is accurate and complete and to assure adherence to study protocol. This will allow for identification of protocol deviations and areas in which practice can be improved. Audits will be done on all paper CRFs, which include the subject's informed consent form, ICF notes, subject eligibility, medical records, concomitant medication list, laboratory results, study procedures, visit notes, investigator notes, adverse event forms, subject drug diary, study drug accountability, and visit schedule. Proper filing of required regulatory documentation and subject CRFs, correct transcription of data, which will include checking for appropriate units of measure and legibility, will be monitored.

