8.2 Criteria for protocol review

Safety related criteria will be in place for continued dosing of subjects. If any of the criteria, listed below, are met, all available data will be reviewed by the principal investigator to provide a recommendation regarding subsequent enrollment.

- A serious adverse event (SAE), deemed related to study treatment, occurs.
- Any subject on treatment experiences bleeding (major or spontaneous).
- Any subject on treatment experiences a Common Terminology Criteria for Adverse Events (CTCAE; v4.03) Grade 3 (or higher) event, deemed related to study treatment.
- Any other event that occurs in a subject on active treatment that is deemed to pose an unacceptable risk to other subjects in the study.

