8.3.3 Adverse Events Collection

Identification of adverse events is important in monitoring for patient safety. Adverse events will be collected during each study visit using a combination of modalities which include, spontaneous reporting of AEs by the patient in response to an open question from study personnel, observation, physical examination, or other diagnostic procedures performed during the study. All subjects will be instructed to report any new or worsening signs and symptoms or clinical events. Adverse events will be reported and assessed for clinical significance by the investigator. Unscheduled clinic visits, additional safety laboratory tests, and other diagnostic procedures may be necessary as recommended by the investigator to evaluate subject safety and to further investigate AEs reported by subjects in-between scheduled clinic visits.

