8.8.4 Procedures for Recording and Reporting of Adverse Events

8.8.4.1 All AEs will be reported to the principal investigator and medical monitor for evaluation. For both serious and non-serious AEs, the investigator has the primary responsibility for AE identification, documentation, grading, and assignment of attribution to the study treatment/intervention. The sponsor will consider the investigator's view when assessing the safety of the drug and determining whether to report expeditiously to the FDA and other regulatory agencies.

8.8.4.2 AEs occurring from the start of study medication administration through the last day of study participation must be recorded on the AE CRF with the following information:

- The intensity grade (grade 1, 2, 3, 4, 5; see CTCAE v4.03 grading)
- The relationship to the study drug(s)

- Attribution: An assessment of the relationship between the AE and the medical intervention (i.e., study drug administration). After naming and grading the event, the clinical investigator must assign an attribution to the AE using the following attribution categories:

RELATIONSHIP	ATTRIBUTION	DESCRIPTION
Unrelated to study treatment/intervention	Unrelated	The AE is clearly NOT related to the study treatment/intervention
	Unlikely	The AE Is doubtfully related to the study treatment/intervention
Related to study treatment/intervention	Possible	The AE may be related to the study treatment/intervention
	Probable	The AE is likely related to the study treatment/intervention
	Definite	The AE is clearly related to the study treatment/intervention

- The duration (start and end dates or if continuing at final exam)
- Occurrence (known risks for study drug/s, underlying illness or population)
 - Expected
 - Unexpected
- Other contributing causes
- Action taken with study drug
- Any other actions in response to event
- Outcome
 - Death related to AE
 - Recovered/resolved with sequelae
 - Not recovered/resolved
 - Recovered/resolved without sequelae
 - Recovering/resolving
 - Intervention for AE continues
 - Unknown
- Whether it constitutes a serious adverse event (SAE)

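### Section 8.8.7 bars collection of non-serious adverse events that do not stop treatment, contradicting 8.8.4 and the visit-by-visit collection

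*Combined protocol and SAP*

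**What the plan says.** Section 8.8.7, the second of two sections titled AE Grading Scale, ends with: "Non-serious AEs which do not lead to discontinuation of study medication will not be collected". The sentence before it says that non-serious events causing permanent discontinuation are entered in the CRF but need no expedited reporting.

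Section 8.8.4 is the section on recording and reporting. Section 8.8.4.1 sends all AEs to the principal investigator and medical monitor, and adds: "For both serious and non-serious AEs, the investigator has the primary responsibility for AE identification, documentation, grading". Section 8.8.4.2 says: "AEs occurring from the start of study medication administration through the last day of study participation must be recorded on the AE CRF". The required fields include CTCAE grade 1 to 5, the action taken with study drug, and whether the event is serious.

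On collection, section 8.3.3 says: "Adverse events will be collected during each study visit using a combination of modalities". Section 8.8.5 has AEs sought by open questioning at each visit. Table 1 marks AEs at run-in (Groups 2-4) and at Visits 2 to 6 (all groups), and the lists in 9.2.2 to 9.2.7 repeat this. Sections 8.8.3 and 8.8.6.1 have bleeding documented by BARC type, and the scale in Appendix A includes non-actionable type 1 bleeding.

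**The concern.** The protocol gives two incompatible instructions on which AEs enter the database. A coordinator who records a mild, non-serious event that does not stop treatment follows 8.8.4.2 and breaks 8.8.7. One who leaves it out does the reverse.

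The synopsis presents the trial as a safety as well as a pharmacodynamic study. Its sections 8.6.1.3.3 and 8.6.1.3.4 list anemia, depression, iron deficiency and oculomotor disturbances as vorapaxar reactions, and mild forms of these are the kind of event 8.8.7 would leave out. The periodic safety reviews in 8.1.2 could also be made on an incomplete record. That section says: "The review process will be initiated after enrolling the first 10 subjects and every 10 subjects thereafter". Events not recorded at the visit may not be recoverable later.

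**Working it through.** The plan gives no figure on this point, so the check sets the current texts side by side.

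| Section | Rule | Fits 8.8.7? |
|---|---|---|
| 8.8.4.1 | All AEs go to the principal investigator and medical monitor | No |
| 8.8.4.2 | AEs from start of study medication to last day of participation go on the AE CRF | No |
| 8.3.3, 8.8.5, Table 1, 9.2.2-9.2.7 | AEs collected or sought at each visit | No |
| 8.8.4.2 fields (grade, seriousness) | Separate serious from non-serious events | Yes, because 8.8.7 also keeps some non-serious events |
| 8.1.2, 8.8.6 | Monitor reviews study-related AEs; detected AEs are followed up | Not decisive, because these concern review and follow-up |
| 8.8.3, 8.8.6.1, Appendix A | Bleeding documented by BARC type | Conflict by implication only |

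**Could 8.8.7 concern expedited reporting only?** Its preceding sentence already separates CRF capture from expedited reporting, and the sentence at issue then speaks of collection. In context it limits what is captured.

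**What would be lost while study drug is taken?** Section 8.4 stops treatment for any serious AE, major or spontaneous bleeding, CTCAE grade 3 or higher, or allergic reaction, among other reasons. Events meeting these criteria stay recordable under 8.8.7. What drops out is the non-serious event that meets none of them, mainly grade 1-2. Non-major, non-spontaneous BARC type 1-2 bleeds drop out too, unless the BARC sentences are read as a separate bleeding rule.

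**Are the review triggers affected?** Three of the four triggers in 8.2 are a related serious AE, major or spontaneous bleeding, and a "Grade 3 (or higher) event, deemed related to study treatment". All three are also 8.4 stopping criteria, so 8.8.7 does not exclude them during treatment. The fourth, an event judged an unacceptable risk to other subjects, has no exact counterpart in 8.4.

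**What happens after Visit 4?** Vorapaxar stops, and only Groups 2-4 receive further study drug (9.2.5, 9.2.6). Group 1 then has no study medication to discontinue. Read literally, 8.8.7 excludes every non-serious AE arising in Group 1 after that point, whatever its grade. Table 1 still schedules 25 × 2 = 50 Group 1 collections at Visits 5 and 6. Groups 2-4 could still discontinue aspirin or clopidogrel, so capture would differ between groups.

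**Scope of the conflict** (Table 1, AE row; 25 subjects per group):

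- Group 1: 25 × 5 (Visits 2-6) = 125
- Groups 2-4: 75 × 6 (run-in and Visits 2-6) = 450
- Total: 125 + 450 = 575 planned collections
- Safety reviews at 10, 20, …, 100 subjects: 100 / 10 = 10

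**The case against.** The best defence is that the protocol as a whole points to full collection. The sections titled for recording and collection say so, and the outlier is one sentence under a duplicated heading, so a sensible site would probably record everything. The people who conduct the safety reviews are also the ones to whom 8.8.4.1 sends all AEs, so at a single site they could know of events missing from the CRF. This is fair, and it makes the effect on the reviews conditional on 8.8.7 being applied. It does not remove the contradiction, because the sentence is current text and no section ranks the rules.

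Some supporting evidence is also weaker than it first looks. The seriousness and grade fields are needed under either rule. The BARC conflict is only implied, since those sentences could stand as a specific rule for bleeding, although no separate bleeding record is described. Both points stand. The direct conflict rests on 8.8.4.1, 8.8.4.2 and the visit-level collection rules, which suffice.

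Finally, sections 5 and 6 define no AE endpoint or safety analysis, so no planned inference changes. That also stands, and it limits the weight of the point.

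**Conclusion.** The contradiction is real, and 8.8.7 is wrong as written: it cannot be reconciled with 8.8.4.1, 8.8.4.2 or collection at each visit. It should be fixed, though it does not threaten the primary analysis.

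If 8.8.7 is applied, non-serious AE counts are understated in all four groups. On treatment the gap is mainly in grade 1-2 events; in Group 1 after Visit 4 it can include any non-serious event. How many events would be lost cannot be estimated, because the documents give no AE rate and no grade or BARC distribution. The 575 collections and 10 reviews assume exactly 100 enrolled subjects who all complete. Since 8.5 does not replace withdrawn subjects, the number of collections would fall with any dropout. Confidence is high for the CRF conflict and lower for the bleeding record.

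**What to change.** Delete the last sentence of 8.8.7 and replace it with:

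> All AEs, including non-serious AEs that do not lead to discontinuation, are recorded on the AE CRF as specified in 8.8.4.2, with a BARC type for every bleeding event. Non-serious AEs do not require expedited reporting. The SAE reporting window is given in 8.8.8.

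The preceding sentence, on non-serious events causing permanent discontinuation, then becomes redundant. It is not inconsistent with the new text, but removing it in the same edit would avoid any hint of a narrower rule. The window in 8.8.8 (from consent until 28 days after participation stops) is unchanged.

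The cost is one replaced sentence. The AE form, the questioning at visits and the BARC documentation are already planned, so no visit, sample or analysis is added. Resolving the conflict the other way would mean rewriting 8.8.4, 8.3.3, 8.8.5, Table 1 and the visit lists.

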8.8.8 SAE Reporting

To ensure subject safety, every SAE, regardless of suspected causality, occurring after the subject signs informed consent and until 4 weeks (28 days) after the subject has stopped study participation must be reported to the principal investigator within 24 hours of learning of its occurrence. Recurrent episodes, complications, or progression of the initial SAE must be reported as follow-up to the original episode, regardless of when the event occurs. An SAE that is considered completely unrelated to a previously reported one should be reported separately as a new event. Information about all SAEs is collected and recorded on the Serious Adverse Event Report Form. The investigator must assess the relationship to study drug and complete the SAE Report. The original copy of the SAE Report Form must be kept with the case report form documentation at the study site.

The follow-up information should describe whether the event has resolved or continues, if and how it was treated, and whether the subject continued or withdrew from study participation.

If the SAE is not previously documented in study drug/s Package Insert (new occurrence) and is thought to be related to the Zontivity (vorapaxar), the investigator may urgently require further information from the investigator for Health Authority reporting. MERCK or designee may need

to issue an IND Safety Letter (Investigator Notification) to inform all investigators involved in any study with the same drug that this SAE has been reported.

The investigator is responsible for promptly notifying the institutional review board (IRB) of all SAEs, including any significant follow-up information. In agreeing to the provisions of this protocol, the investigator accepts the legal responsibilities for prompt notification of any SAE.

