8.8.6 Adverse Event Treatment

All AEs should be treated appropriately and managed as according to standard of care, at the discretion of the investigator. The action taken to treat the AE should be recorded on the AE CRF. A detected AE should be followed until its resolution or until the subject completes the study. Assessment should be made at each visit (or more frequently, if necessary) of any changes in severity, relationship to the study drug, the interventions required to treat it, and the outcome.

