9.2.7 Visit 6/ End of Study

The subject will report to research site 14 ± 3 days of visit 5. The day prior to the visit, the study coordinator will call the subjects for visit 6 instructions. Remind the subjects not to ingest any high fat foods and to hold EC ASA and/or clopidogrel (for groups 2, 3, and 4) the morning of scheduled visit, and to return any unused study drug. The following procedures will be performed during this visit:

- Vital signs (blood pressure, heart rate) will be obtained after the subject has been in a sitting position for at least 5 minutes.
- Confirm compliance with dietary restrictions (high fat foods)
- Determine adverse event occurrence and follow-up on previously reported adverse events.
- Collection of concomitant medications.
- Blood/urine samples will be obtained for and PD measurements.
- Return unused study drug for groups 2, 3, and 4.
- Study drug accountability
- If applicable, instruct subject to return to original ASA and/or clopidogrel dose.

At the end of the study, all subjects will return to their original standard of care treatment and for any medical treatment questions, will be instructed to resume follow-up with their primary care team.

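### SAE reporting runs 28 days past the end of participation, but no contact is scheduled in that period for completers or for subjects removed early

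*Combined protocol and SAP*

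**What the plan says.** - **SAE window (section 8.8.8).** It covers events "occurring after the subject signs informed consent". Every SAE from then "until 4 weeks (28 days) after the subject has stopped study participation must be reported to the principal investigator within 24 hours" of the site learning of it. A later recurrence, complication or worsening "must be reported as follow-up to the original episode, regardless of when the event occurs", and the follow-up information is to say whether the event resolved or continues.
- **AE window and follow-up.** Section 8.8.4.2: "AEs occurring from the start of study medication administration through the last day of study participation must be recorded on the AE CRF". Section 8.8.6: "A detected AE should be followed until its resolution or until the subject completes the study". Section 8.8.6 makes no exception for SAEs.
- **Last contact.** Table 1 ends at Visit 6/EOS. Under section 9.2.7 subjects go back to their usual treatment and, "for any medical treatment questions, will be instructed to resume follow-up with their primary care team". No later visit, call or records check is listed.
- **Early removal (section 8.4).** Any SAE, any major or spontaneous bleed, and any AE of CTCAE grade 3 or higher are among the reasons to stop treatment and remove the subject from participation. Table 1 has no contact for removed subjects. Section 8.5.1 asks the investigator to provide or refer for medical care, which is not the same as collecting outcomes.
- **Study drugs.** Section 3.1 counts clopidogrel and aspirin as study drugs. Vorapaxar stops at Visit 4 (section 9.2.5). Group 2, enrolled without antiplatelet therapy, is dispensed clopidogrel at Visit 5 and returns what is left at Visit 6 (sections 9.2.6 and 9.2.7).

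**The concern.** The plan sets a reporting window but describes no way of finding events in its last 28 days. The 24-hour clock starts when the site learns of an SAE, and after participation stops nothing scheduled lets the site learn of one. For that period, a record with no SAE cannot be told apart from a subject nobody asked.

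What is at stake is safety information, not efficacy. Section 8.2 makes a treatment-related SAE a trigger for reviewing further enrolment, and section 8.1.2 sets safety reviews after every 10 subjects. Both depend on SAEs reaching the site.

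A second problem is that sections 8.8.6 and 8.8.8 give different end points for following an SAE that is still open when participation stops.

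**Working it through.** **1. Check the visit calendar against the plan's own figure.** Days count from the first vorapaxar dose (Visit 2 = day 0). Visit 4 is at 30 ± 7 days; Visits 5 and 6 each follow by 14 ± 3 days (Table 1).

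Visit 5 = 30 + 14 = day 44. This matches the 44 days in section 8.3.4, the only cumulative visit day that the protocol states.

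**2. Extend to the end of the SAE window (completer).**

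- Visit 6 = 30 + 14 + 14 = day 58.
- End of window = 58 + 28 = day 86.
- Share after last scheduled contact = 28/86 = 32.6%.
- Shortest visit windows: 23 + 11 + 11 + 28 = 73; 28/73 = 38.4%.
- Longest visit windows: 37 + 17 + 17 + 28 = 99; 28/99 = 28.3%.

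Section 9 puts Visit 4 at 3-4 weeks instead. That gives 21 + 14 + 14 + 28 = 77 days (28/77 = 36.4%) to 28 + 14 + 14 + 28 = 84 days (28/84 = 33.3%).

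**3. Vary the start of the window.** Section 8.8.8 starts it at consent. Table 1 allows Visit 2 from 3 to 28 days after screening. At nominal visit dates:

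| Counted from | Length in days | Share without scheduled contact |
|---|---|---|
| First vorapaxar dose | 86 | 28/86 = 32.6% |
| Consent, 3 days before Visit 2 | 86 + 3 = 89 | 28/89 = 31.5% |
| Consent, 28 days before Visit 2 | 86 + 28 = 114 | 28/114 = 24.6% |
| Vorapaxar stop (Visit 4) | 86 - 30 = 56 | 28/56 = 50.0% |

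**4. Coverage after each drug stops.**

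- *Vorapaxar, completers.* Visit 6 is 14 + 14 = 28 days after Visit 4 (22 to 34 over the visit windows). Scheduled visits cover the nominal 28 days off vorapaxar.
- *Clopidogrel, Group 2 (25 planned).* Study clopidogrel runs to Visit 6. The part of the SAE window after it ends is exactly the 28 days without scheduled contact.
- *Subjects removed under section 8.4.* Treatment and participation stop together, so the 28-day window coincides with their first 28 days off all study drug, and none of it has a scheduled contact.

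**5. Compare the two follow-up rules.** For an SAE open at Visit 6, section 8.8.6 read alone allows follow-up to end there. Section 8.8.8 asks whether it resolved and sets no time limit on reporting recurrence or progression. For a removed subject, who never completes the study, the end point in section 8.8.6 is undefined. Neither section says which governs.

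**The case against.** The strongest reply is that reporting is passive, not absent. The duty in section 8.8.8 is triggered by knowledge of the event. Section 8.3.3 has all subjects told to report new or worsening clinical events, section 8.3.1 allows review of medical records under consent, and section 9.2.1 mentions access to the hospital record system. None of these is said to stop at Visit 6. This stands: a reader might infer that the last 28 days are unobserved, and the documents do not support that. Nor are these routes said to continue. Sections 9.2.3 and 9.2.4 tell subjects to contact the site about adverse reactions, and section 9.2.7 has no such instruction.

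Other points on that side:

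- *Primary care.* The handover in section 9.2.7 concerns treatment questions. It does not redirect SAE reporting away from the site. This stands.
- *SAE follow-up.* A reader might infer from section 8.8.6 that an SAE found at Visit 6 gets no follow-up. Section 8.8.8 is the specific SAE rule and points the other way. What remains is an unreconciled conflict, not a rule against follow-up.
- *Completers.* Under section 8.4 a subject with an SAE or major bleed before Visit 6 should already have been removed, so few completers should have one open at Visit 6. This stands, and it moves the weight of the point to removed subjects.
- *Days are not events.* The share is of calendar time. For vorapaxar in completers, Visits 5 and 6 already cover the nominal month off drug. This stands.
- *No analysis is affected.* The endpoints in section 5.2 are pharmacodynamic, biomarker and endothelial measures, and no safety rate over this window is planned. This stands.

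**Conclusion.** The point holds as a minor one about safety data collection. The protocol requires SAE reporting for 28 days after participation stops and schedules no contact in those days for anyone.

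In a completer this is 33% of the window from first vorapaxar dose (28.3-38.4% over the visit windows), or about 25-32% from consent at nominal visit dates. A reader might call it the last third of the window. That fits only a count from first vorapaxar dose, whereas section 8.8.8 counts from consent.

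A reader might also infer that the month after vorapaxar goes unmonitored. In completers it does not. The gap matters most for subjects removed for an SAE or bleeding, and for Group 2 after study clopidogrel ends. Separately, sections 8.8.6 and 8.8.8 need to be reconciled.

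Two assumptions underlie this: participation stops at Visit 6 or at removal, which the protocol does not define, and no contact exists beyond those in Table 1 and section 9.2. The documents give no expected SAE rate, so the number of events that might be missed cannot be estimated.

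**What to change.** 1. Add to Table 1 one coordinator telephone contact 28 days after participation stops, for completers and early-removed subjects alike, except where consent is withdrawn. It asks about hospital admissions, bleeding and other serious events. Tying it to the end of participation, not to Visit 6, is what makes it reach removed subjects.
2. State in section 8.8.8 that participation stops at Visit 6 or at removal, and that the call does not extend it. Otherwise the call could be read as moving the 28-day window.
3. Reconcile section 8.8.6 with section 8.8.8, so that follow-up of SAEs open when participation stops is governed by section 8.8.8.

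The cost is one short call per subject, about 100 in all (4 groups of 25), by coordinators who already telephone subjects before Visits 2, 4, 5 and 6, plus a Table 1 column and two or three sentences. Data for the last subject close 28 days later. If the call is not adopted, the protocol should at least say that SAE capture after participation stops is passive.
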